14.8 Determination of sample size

14.8.1 Determination of sample size for double-blind for plaque PSO

A total of 125 subjects will be randomly assigned in a 2:2:1 ratio to the following treatment groups:

- CZP 200mg Q2W (with CZP 400mg loading dose at Weeks 0, 2, and 4) (n=50)
- CZP 400mg Q2W (n=50)
- Placebo (n=25)

Both CZP doses will be evaluated for superiority to PBO. The assumed response rates for PASI75 at Week 16 are 75%, 70%, and 15% for CZP 400mg Q2W, CZP 200mg Q2W, and PBO, respectively. Under these assumptions, 43 subjects for each CZP groups and 22 for PBO group were required to detect a difference between CZP (either dose) group and the PBO group with

the power of at least 98% and a 2-sided significance level of 0.025. To allow a margin for some subjects to be excluded from analysis and to consider ensuring the safety assessment cases, the target number of subjects is set to 50 subjects for each CZP groups and 25 for PBO group. The power to detect a statistically significant difference between CZP (either dose) and PBO based on PASI75 given the above assumptions and using a 2-sided test significance level of 0.025 is >99%.

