1. Create a data set, one for each treatment group, of subjects with observed values and those needing estimation by MCMC. The missing PASI values in each data set will be filled in using the MCMC method with a total of 75 sets of imputation being performed. The seed used for these imputations will be 958 (Note: All other multiple imputation procedures described in this SAP will use this same seed as well). The procedure will sequentially estimate an imputation model for the PASI score at each post-Baseline visit (up to Week 16) where PASI is collected, with prior biologic exposure, and Baseline score as predictors. Note that PASI scores at earlier visits will also be used as predictors for the model of PASI at later visits. The resulting data sets for each treatment arm will be combined into one complete data set based on each of the 75 imputations.

Note: If one treatment group is complete, so without any missing values, then this treatment group is excluded from MCMC imputation and the observed data will be duplicated 75 times and rejoined to the imputed data set.

Note: The imputation model based on the MCMC method will only allow continuous variables as predictors. Therefore, prior biologic exposure will be re-coded as indicator variables (with values of 0 or 1). Because prior biologic exposure has just 2 levels, only one indicator variable will be needed.

2. For each complete imputed data set, the dichotomous responder rate based on the PASI scores will be computed. Each complete imputed data set will then be analyzed based on a logistic regression model with factors of treatment group and prior biologic exposure (yes/no).

Note: For derivation of PASI75 response, the imputed PASI value will be compared directly to the observed Baseline PASI value to determine whether or not a reduction of at least 75% was achieved. If values outside of the pre-defined range of values for PASI (0-72) are imputed, they will be cut off as appropriate after the multiple imputation procedure but before deriving the responder variables. For example an imputed PASI value of -0.5 would be changed to 0 before deriving the PASI75 responder variable.

3. The Week 16 results from the logistic regression analysis of each of the 75 imputed data sets will be combined into a single inference using SAS PROC MIANALYZE.

Some key points to consider relative to the calculation of the odds ratios and corresponding confidence intervals are noted below:

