In addition to calculating the odds ratio, associated CIs, and p-values for the pairwise comparisons of each CZP treatment group with PBO, the estimated proportion of responders (eg, estimated responder rate) and the difference in the proportion of responders between each CZP treatment group and PBO will be estimated, and 2-sided 95% CIs will be created for each difference. The creation of these estimates will be completed for each CZP treatment group using the process detailed below:

1. Use the logistic regression model to calculate:
 - a. Least squares mean estimates of the log odds of CZP (G_C) and PBO (G_P), as well as their corresponding standard errors (S_C and S_P , respectively)
 - b. Standard error of the least squares mean estimate of the log odds ratio (S_R)
2. Compute estimates for predicted proportions using the following transformations:

$$P_C = \exp(G_C) / (1 + \exp(G_C))$$

$$P_P = \exp(G_P) / (1 + \exp(G_P))$$

The difference in proportions is then given by:

$$D = P_C - P_P$$

3. Estimate the standard error of D by:

$$S_D = \sqrt{P_C^2 (1 - P_C)^2 S_C^2 + P_P^2 (1 - P_P)^2 S_P^2 + P_C (1 - P_C) P_P (1 - P_P) S_R^2 - P_C (1 - P_C) P_P (1 - P_P) (S_C^2 + S_P^2)}$$

The Markov Chain Monte Carlo (MCMC) method for multiple imputation, as previously outlined, will be used to account for missing values of PASI. This method will create multiple complete data sets which may be analyzed with the process described above. An estimate for the difference in proportions, D, and corresponding standard error, SD, will be computed for each complete dataset.

The results from these analyses will be combined into a single 2-sided 95% confidence interval using SAS PROC MIANALYZE.

In cases where one treatment group has either no responders or only responders, exact logistic regression will be used to calculate the odds ratio with its corresponding confidence interval and p-value. The exact logistic regression will include treatment, and prior biologic exposure as in the primary model. The following procedure will be used to obtain these estimates:

1. Obtain the odds ratio and lower 2-sided confidence limit (based on $\alpha=0.05$ for a 95% confidence interval and $\alpha=0.025$ for a 97.5% confidence interval) for each imputation from PROC LOGISTIC using the EXACT statement and ESTIMATE=BOTH option.

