2. Take the log of the exact odds ratio for each imputation and calculate $[\log(\text{odds ratio}) - \log(\text{lower/upper CL})] / Z_{\alpha/2}$ for each imputation as the standard error. Note the upper/lower CL will not be used as it is undefined for cases where there are no/only responders in a treatment group.
3. Use PROC MIANALYZE to combine the log odds ratio estimates and standard errors into a single estimate and corresponding standard error.
4. Exponentiate the estimate obtained from the previous step to obtain the odds ratio and calculate the confidence interval as $OR * \exp(\pm (SE * Z_{\alpha/2}))$ where OR is the odds ratio estimate and SE is the combined estimate of the log odds ratio from PROC MIANALYZE.

This method of exact logistic regression will be used for any endpoint in the statistical hierarchy when one treatment group has no responders.

The calculation of responder rates and the differences in proportion of responders is also impacted when at least one treatment group has no/only responders. In this case, the responder rate will be calculated as the simple proportion of responders for each treatment group across all 75 imputed data sets. The difference in proportions between each CZP group and placebo is calculated for each imputation. The standard error of the difference in proportions for a given CZP group versus placebo is then calculated for each imputation. The standard error is calculated as:

$$\sqrt{\hat{p}(1 - \hat{p})\left(\frac{1}{n_1} + \frac{1}{n_2}\right)},$$

where

$$\hat{p} = \frac{Y_1 + Y_2}{n_1 + n_2}.$$

Note that Y_1 and Y_2 are the number of responders in the placebo and given CZP group, respectively, while n_1 and n_2 are the total number of subjects in each group, respectively. The estimates for the difference in proportion of responders and the standard error above are passed into PROC MIANALYZE so that the overall difference in proportion of responders and the 95% confidence interval can be calculated.

Some additional considerations in the event that there are no/only responders in a given treatment group are as follows:

- If there are no/only observed responders in any treatment group, then none of the calculations described above will be done and the responder rates will be presented as 0/1 while all other statistics will not be calculated.

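### Week 16 responder rates and differences taken from back-transformed logit least-squares means do not estimate the proportions in the Full Analysis Set unless prior biologic exposure has no effect

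*SAP*

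**What the plan says.** The primary analysis of PASI75 at Week 16 (SAP 8.1.2) is a logistic regression with fixed effects for treatment and prior biologic exposure (yes/no), fitted to each of 75 imputed data sets. The odds ratio, its confidence interval and the p-value come from this model.

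In addition, the SAP reports an estimated proportion of responders per arm and the difference between each CZP arm and placebo with a 95% CI. These start from "Least squares mean estimates of the log odds of CZP" (G_C) and of placebo (G_P). Each is inverted as P = exp(G)/(1+exp(G)), and D = P_C − P_P is pooled with its standard error by PROC MIANALYZE. The SAP gives no weights for averaging over the two exposure strata, and it does not standardise over the trial's stratum mix.

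The method carries over to PGA response and PASI90 (SAP 8.2.1, 8.2.2) and to the by-visit PASI and PGA rates up to Week 16 (SAP 8.3.1, 8.3.2). If an arm has no or only responders, it is replaced: "the responder rate will be calculated as the simple proportion of responders for each treatment group across all 75 imputed data sets".

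**The concern.** A reader will take an estimated proportion of responders to be the proportion expected in the trial population under that treatment. A back-transformed least-squares mean differs from that for two reasons.

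- **Weights.** A least-squares mean over a two-level factor gives each level a weight of one half unless observed margins are requested. If far fewer than half the subjects had prior biologics, the exposed stratum counts for too much.
- **Scale.** The inverse logit of an average log odds is not the average of the probabilities. This remains whatever the weights.

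Responder rates and risk differences are the figures clinicians will quote, so they should be the quantity they are named for. The fallback to simple proportions, by contrast, does target the population proportion. If one endpoint triggers it and another does not, two lines of the same table rest on different quantities.

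**Working it through.** **The plan's own figures.** Protocol 14.8.1 states: "The assumed response rates for PASI75 at Week 16 are 75%, 70%, and 15% for CZP 400mg Q2W, CZP 200mg Q2W, and PBO, respectively". It says "43 subjects for each CZP groups and 22 for PBO group were required" for "the power of at least 98% and a 2-sided significance level of 0.025", and that "the target number of subjects is set to 50 subjects for each CZP groups and 25 for PBO group". For 200mg against placebo, power = Φ[(d − z·SE0)/SE1], with d = 0.55 and z = 2.241 (two-sided 0.025).

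- At 43/22: pooled rate (43×0.70 + 22×0.15)/65 = 0.514, SE0 = 0.1310, SE1 = 0.1033. Power = Φ[(0.55 − 0.2937)/0.1033] = Φ(2.48) = 99.3%; Fisher's exact test gives 98.6%.
- At 50/25: SE0 = 0.1224, SE1 = 0.0964. Power = Φ(2.86) = 99.8%; Fisher 99.3%.

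The design figures reproduce, so the planning rates serve as the true rates below.

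**Assumed inputs.** The documents give neither the share π with prior biologic exposure nor its odds ratio for response. Assumed: π = 10-30% (also 50%) and odds ratio 0.33, 0.5, 0.8 or 1.0.

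**Method.** For an arm with true rate p and β = ln(odds ratio):

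1. Solve (1 − π)·expit(α) + π·expit(α + β) = p for α.
2. Equal-weight rate: expit(α + 0.5β).
3. Observed-margin rate: expit(α + πβ).
4. Standardised rate: the left side of step 1, which equals p.

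**Worked case, π = 20%, odds ratio 0.33** (β = −1.109; differences taken before rounding):

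- 200mg: α = 1.101, so the strata respond at 75.0% and 49.8%, and 0.8×75.0 + 0.2×49.8 = 70.0%. Equal weights: expit(1.101 − 0.554) = expit(0.547) = 63.3%.
- Placebo: α = −1.575, so the strata respond at 17.2% and 6.4%, averaging 15.0%. Equal weights: expit(−2.129) = 10.6%.
- Difference: 52.7 points against a true 55. Observed margins: 70.7% and 14.2%, difference 56.4.

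**Range, 200mg against placebo (true 70.0%, 15.0%, difference 55.0):**

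| Prior use | Odds ratio | 200mg, equal | Placebo, equal | Difference, equal | Difference, observed margins |
|---|---|---|---|---|---|
| 10% | 0.33 | 60.3 | 9.9 | 50.5 | 55.8 |
| 10% | 0.5 | 64.0 | 11.7 | 52.4 | 55.3 |
| 20% | 0.33 | 63.3 | 10.6 | 52.7 | 56.4 |
| 20% | 0.5 | 65.8 | 12.3 | 53.5 | 55.6 |
| 30% | 0.33 | 66.2 | 11.5 | 54.7 | 57.0 |
| 30% | 0.5 | 67.4 | 12.9 | 54.5 | 55.8 |
| 10-30% | 0.8 | 68.1-69.1 | 13.9-14.4 | 54.2-54.7 | 55.0-55.1 |
| any | 1.0 | 70.0 | 15.0 | 55.0 | 55.0 |

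For 400mg (true 75%, difference 60) at odds ratios 0.33-0.5 and 10-30% prior use, equal weights give 66.3-72.8% and a difference of 56.5-60.4. At 50% prior use the sign turns: the 200mg difference becomes 57.6 at 0.33 and 56.0 at 0.5.

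Observed margins keep each arm's rate within about 1.1 points of truth in the table. The two arms err in opposite directions, however, so the difference overshoots. At 30% prior use it is further from 55 than the equal-weight difference, in which the arm errors largely cancel.

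**Standard error.** Since Cov(G_C, G_P) = (S_C² + S_P² − S_R²)/2, the SAP's S_D is exactly the delta-method expression. In the worked case both give 0.0915. The variance formula is right; the issue is only what is estimated.

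**How likely the switch to simple proportions is.** The chance of no responders among 25 placebo subjects is 0.85^25 = 1.7% at the planned PASI75 rate. At the 1.7% placebo PGA rate in Protocol Table 5-2 (Week 12, a different study) it is 0.983^25 = 65%. So PGA could fall back while PASI75 does not.

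**The case against.** The strongest reply is that these estimates are supplementary. The effect measure named in Protocol 14.3.1 is the odds ratio, and SAP 8.1.2 presents the rates and differences on top of it. A reader might infer that the primary result or the success criterion is biased. The documents do not support that: the tests use the log odds ratio, so the odds ratios, p-values and fixed-sequence procedure are untouched. Nor is the least-squares-mean rate wrong in itself. It is a legitimate conditional quantity, and it misleads only when read as the FAS proportion.

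Crude rates are also available. Observed rates are tabulated in SAP 8.1.3, 8.3.1 and 8.3.2, and the final-analysis maintenance rates are simple proportions. This stands, but the crude rates do not carry the primary handling of missing data or an adjusted difference with a CI.

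Equal weighting is the usual meaning of a least-squares mean but is not written in the SAP. This also stands, and the sizes quoted for equal weights depend on it. The scale problem does not.

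The strength of the covariate is unknown. SAP 4.1 says only that it may affect efficacy, and exclusion criterion 24 bars primary failures and more than two prior biologics, so a strong adverse effect cannot be presumed. The shift in the difference, 0.3 to 4.5 points at odds ratios 0.33-0.5, is also small beside its sampling SE of about 9.6 points at 50/25. Both are fair limits on size, but a larger sample would not remove this shift.

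**Conclusion.** The point holds as a matter of what is estimated. As specified, the model-based rates and differences do not target the FAS proportions unless prior biologic exposure has no effect or the errors happen to cancel. Under equal weights, the planning rates, 10-30% prior use and an odds ratio of 0.33-0.5, the 200mg rate is understated by 2.6 to 9.7 points, the placebo rate by 2.1 to 5.1, and the difference by 0.3 to 4.5. At an odds ratio of 0.8 the difference moves by 0.3 to 0.8 points, and at 1.0 by nothing.

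Two further readings go too far. One is that the method always understates the effect; at 50% prior use it overstates it. The other is that rates are never comparable across endpoints; they target different quantities only when an arm has no or only responders, and that switch is pre-specified. This is a cheap improvement to a supplementary estimate, not a threat to the trial's conclusion.

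**What to change.** In each imputed data set, use the fitted logistic model to predict every FAS subject's response probability under CZP and again under placebo. Average each set over the FAS, take the difference with a delta-method SE, and pool with PROC MIANALYZE. Apply this to PASI75, PASI90, PGA response and the by-visit PASI and PGA rates through Week 16, wherever the logistic model can be fitted.

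It cannot serve every case: with no or only responders in an arm, the maximum-likelihood fit does not exist. Keep the simple-proportion fallback of SAP 8.1.2 there. The fallback then targets the same population proportion as the standardised rates, so endpoints stay comparable. If any least-squares-mean rates are kept, state their weights and label them as conditional.

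The cost is a small amount of extra programming. No new data are needed, and the odds ratios and hypothesis tests do not change.

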8.1.2 Primary analysis of the primary efficacy variable

The primary analysis for the PASI75 response at Week 16 will be based on a logistic regression model for the FAS which will include fixed effects for treatment group and prior biologic exposure (yes/no). Prior biologic exposure was selected as a fixed effect in the logistic regression model as it is a stratification variable for randomization and because it may have an impact on efficacy. The odds ratio, associated confidence interval, and p-value

will be presented. If convergence is not obtained due to having only or no responders in one or more treatment groups, then an exact logistic regression will be applied and odds ratio, associated exact confidence interval, and exact p-value will be determined. If the logistic regression model is unable to converge, then prior biologic exposure may be dropped from the model to facilitate convergence. This model is used when the sample size is too small for a regular logistic regression or when some of the cells formed by the outcome and categorical predictor variable have no observation.

The Markov Chain Monte Carlo (MCMC) method for multiple imputation will be used to account for missing values in the primary analysis of PASI75 at Week 16. The multiple imputation procedure for PASI75 will be based on the actual PASI score.

For derivation of PASI75 response, no rounding will be performed. That is, the imputed Week 16 PASI value will be compared directly to the observed Baseline value to determine whether or not a reduction of at least 75% was achieved.

Each CZP dose will be compared against PBO to establish superiority over PBO and will be tested sequentially at an alpha of 0.025 as outlined in Section 4.5.

Multiple imputation and the subsequent analysis will involve the 3 tasks described below:

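### When one group has no (or only) responders and the imputations differ, the SAP's 'exact' CI and p-value are a Wald result from a one-limit standard error whose alpha is not fixed

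*SAP*

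**What the plan says.** SAP 8.1.2 analyses each binary endpoint by logistic regression (treatment, prior biologic exposure) in 75 imputed data sets and pools the log odds ratios in PROC MIANALYZE. If the model does not converge because a group has only or no responders, it moves to exact logistic regression, from which "odds ratio, associated exact confidence interval, and exact p-value will be determined".

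A four-step procedure follows:

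- Take the exact odds ratio and its lower limit in each imputation, with alpha 0.05 for a 95% interval and 0.025 for a 97.5% interval.
- Define the standard error as the log odds ratio minus the log of the limit, divided by the normal critical value. The other limit is dropped: "Note the upper/lower CL will not be used as it is undefined for cases where there are no/only responders in a treatment group".
- Pool the log odds ratios and these standard errors in PROC MIANALYZE.
- Report the odds ratio multiplied by exp(±SE × Z).

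Earlier in the same section, the tabulated p-values are said to be those from PROC MIANALYZE.

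On scope, the section states: "This method of exact logistic regression will be used for any endpoint in the statistical hierarchy when one treatment group has no responders". Shortly afterwards a bullet says: "If there are no/only observed responders in any treatment group, then none of the calculations described above will be done". The next bullet still makes calculations when two groups are affected. A last bullet says that if all imputed data sets are the same, results come from (exact) logistic regression on the observed data.

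**The concern.** In the ordinary route the standard error comes from both Wald limits. These are symmetric on the log scale, so any alpha returns the same standard error. The fallback applies the same idea to an exact limit around an odds ratio whose other limit is infinite. That is not symmetric, which has three consequences:

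- The pooled p-value is a Wald p-value. No rule combines the 75 exact p-values.
- A finite bound is reported where the exact bound is infinite.
- The standard error, and so the p-value, depends on which limit is used. The text allows either and does not say which feeds the test.

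The fallback applies to endpoints in the confirmatory sequence, and PGA is second in it. A confirmatory p-value and interval could then be published as exact when they are not. Separately, the word *any* in the first special-case bullet leaves room to argue that a required hierarchy test is skipped.

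**Working it through.** **Inputs.** Protocol 14.8.1 gives the target size ("50 subjects for each CZP groups and 25 for PBO group") and the 2-sided alpha of 0.025 per dose. Protocol Table 5-2 gives the C87040 Week 12 placebo rate for PGA clear or almost clear, 1.7%.

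**The plan's own figure first.** The protocol says "43 subjects for each CZP groups and 22 for PBO group were required" for "the power of at least 98% and a 2-sided significance level of 0.025". For 70% vs 15% with 43 and 22:

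- Pooled rate = (43 × 0.70 + 22 × 0.15)/65 = 0.514.
- SE under the null = √[0.514 × 0.486 × (1/43 + 1/22)] = 0.131. SE under the alternative = √(0.21/43 + 0.1275/22) = 0.103.
- Power = Φ[(0.55 − 2.241 × 0.131)/0.103] = 99.3%. With continuity correction it is 98.3%, and by Fisher's test 98.6%.

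The statement reproduces. It does not depend on the fallback; it only confirms the inputs.

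**How often the fallback is reached.** P(0 of 25) = (1 − p)^25.

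| Placebo rate | Source | P(0/25) |
|---|---|---|
| 15% | planned PASI75 | 0.017 |
| 1.7% | C87040 PGA, Week 12 | 0.65 |
| 3% | assumption for PGA | 0.47 |
| 1% to 5% | assumption for PASI90 (no rate in the documents) | 0.78 to 0.28 |

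**What the fallback returns.** Take placebo 0/25 and CZP x/50, one data set, no stratum. Given x responders in total, the number on placebo is noncentral hypergeometric with parameter OR.

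- The median-unbiased OR solves P(0 on placebo) = 0.5.
- The exact lower limit solves P(0 on placebo) = alpha/2. The upper limit is infinite.
- SAP SE = (log OR − log lower limit)/Z. Wald p = 2[1 − Φ(log OR/SE)].

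For x = 10, OR = 8.34 and log OR = 2.121.

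- 97.5% limit 1.003: SE = (2.121 − 0.003)/2.241 = 0.945; 2.121/0.945 = 2.244; p = 0.0248.
- 95% limit 1.252: SE = (2.121 − 0.225)/1.960 = 0.967; 2.121/0.967 = 2.193; p = 0.0283.

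| x/50 | SAP p, 97.5% limit | SAP p, 95% limit | Exact p, twice one-sided | Fisher p |
|---|---|---|---|---|
| 9 | 0.0371 | 0.0415 | 0.0399 | 0.0251 |
| 10 | 0.0248 | 0.0283 | 0.0248 | 0.0255 |
| 13 | 0.0079 | 0.0096 | 0.0056 | 0.0034 |
| 20 | 0.00065 | 0.00091 | 0.00012 | 0.00007 |

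At x = 20 (OR 22.36) the exact 97.5% interval is 2.90 to infinity; the SAP reports 2.90 to 172.6. For the 95% interval the reported upper limit is 140 (22.36²/3.57).

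**With the stratum.** With an assumed 28% prior-biologic share, x = 10 gives 0.0257 and 0.0293, against an exact 0.0258 (twice one-sided). The gap between the two limits remains, but both values then lie above 0.025.

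**With imputations that differ.** Assume 10 observed CZP responders, 4 missing CZP values each with a 30% chance of response, and placebo 0/25 in all 75 sets. The pooled p is 0.0163 (97.5% limit) or 0.0190 (95% limit).

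**Would Firth regression be better?** Rubin's rules need an estimate and a standard error, so a pooled Firth analysis is also a Wald test. For 13/50, log OR = log(13.5/37.5) − log(0.5/25.5) = 2.91 and SE = 1.49, so p = 0.051. For 20/50, p = 0.017. It first falls below 0.025 at x = 18 (0.0234; x = 17 gives 0.0272), whereas the SAP method with the 97.5% limit does so from x = 10.

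**The case against.** The other side has four good points.

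**Identical imputations are handled.** The last special-case bullet of 8.1.2 sends that case to exact logistic regression on observed data. The single-data-set figures above are therefore approximations to a pooled analysis with little between-imputation variance; they would not themselves be reported. This stands, and it limits the point to imputations that differ.

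**Decisions match when the alphas match.** In one data set, if the limit is taken at the test's alpha, the Wald limit equals the exact limit. Rejection then agrees with the exact interval, and at larger effects the SAP p-value exceeds the exact one. This stands. A reader might infer that type I error is inflated or that the hierarchy is invalid; the calculations do not show that.

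**The fair comparator is twice the one-sided exact p.** It matches an interval that puts alpha/2 in each tail, and against it the gap is smaller than against Fisher (0.0056 rather than 0.0034 at 13/50). This also stands.

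**The *any* bullet probably means all groups.** A reader might infer that the SAP cancels the test whenever placebo alone has no responders. The context is against that: the sentence just before requires the exact method when one group has none, and the next bullet deals with two groups. The wording is loose enough to correct, but the documents do not establish a cancelled test.

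**Conclusion.** The point holds in a limited form. When a group has no or only responders and the imputations differ, the CI and p-value labelled exact are Wald quantities built on one exact limit. The p-value is conservative at the expected effects, the far limit is artificially finite, and the alpha behind the standard error is unspecified.

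That last gap matters only close to the threshold: at 10/50 the choice moves p from 0.0248 to 0.0283, while at 13/50 and above both choices are well below 0.025. The effect is on the accuracy of reported confirmatory results and on pre-specification, seldom on a decision.

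Exposure is plausible for PGA and unlikely for PASI75. It is unknown for PASI90, because no placebo rate is given. The PGA figure assumes that a Week 12 rate from another study carries over to Week 16 here. The p-value conclusion assumes that the MIANALYZE statement, written for the ordinary route, also governs the fallback; the four steps offer no alternative. Normal critical values were used throughout.

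**What to change.** Change the wording of SAP 8.1.2 as follows:

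1. In the first special-case bullet, replace *any* with *all* treatment groups, so that it cannot be read against the sentence requiring the test for hierarchy endpoints.
2. Compute the standard error from the limit at the test's own alpha: 0.025, or 0.05 if alpha has been passed on under SAP 4.5. Take the absolute difference when the upper limit is the finite one; otherwise the standard error is negative.
3. Report the undefined limit as not estimable.
4. Stop calling the pooled CI and p-value exact, and add an exact test on the non-responder-imputed data as a labelled supportive check.

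Do not substitute Firth estimates with Wald standard errors pooled by Rubin's rules. They lie further from the exact result and would lose steps that the current method passes (x = 10 to 17 in the example).

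The cost is a few sentences and one supportive table. SAP 4.3 places the Week 16 analysis in the interim report, and SAP 9.3 already cites interim results. The amendment should therefore record which alpha and which reading of the bullet the interim run used.

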- If there are no/only observed responders in two of the groups, then responder rates will be calculated as described above, but the difference in proportions and odds ratio calculations will be done only for PBO and the CZP group with more than 0 responders.
- If there is a case where all imputed data sets are exactly the same, then combined estimates of the standard error cannot be calculated. Therefore, the results will be based on the actual observed data and on the (exact) logistic regression using this data.

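### SAP 8.1.2: when a group has no or only responders, the 95% CI for the risk difference uses the equal-rates pooled standard error; it is too wide at plausible response rates and not comparable with the ordinary interval

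*SAP*

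**What the plan says.** SAP 8.1.2 adds responder rates and their differences to the odds ratio, "and 2-sided 95% CIs will be created for each difference". There are two routes to the standard error.

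- **Ordinary route.** The step worded "Estimate the standard error of D by" gives a delta-method formula built from each group's own log-odds standard error and that of the log odds ratio.
- **No/only-responder route.** If at least one group is empty or full, the simple difference is taken for each imputation with standard error √[p(1−p)(1/n₁+1/n₂)], where p = (Y₁+Y₂)/(n₁+n₂) pools placebo and the CZP group. These are "passed into PROC MIANALYZE so that the overall difference in proportion of responders and the 95% confidence interval can be calculated".

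For the odds ratio, the section says that if convergence fails "due to having only or no responders in one or more treatment groups, then an exact logistic regression will be applied". It adds: "This method of exact logistic regression will be used for any endpoint in the statistical hierarchy when one treatment group has no responders".

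The first of the closing bullets then reads "If there are no/only observed responders in any treatment group, then none of the calculations described above will be done", and continues that "the responder rates will be presented as 0/1 while all other statistics will not be calculated". The next bullet begins "If there are no/only observed responders in two of the groups, then responder rates will be calculated as described above".

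SAP 8.2.1 and 8.2.2 apply the primary method to PGA response and PASI90, so both routes are open to them.

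**The concern.** The pooled formula is the variance of the difference when the two true rates are equal. Here it is used to build an interval around a difference expected to be large. The ordinary route makes no such assumption, and the SAP gives no reason for switching. One table could then show a PASI75 difference from one route beside a PGA difference from the other, both labelled 95% and not comparable.

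The wording of the first bullet compounds this. If *any* means at least one group, it cancels the rule stated just above it. It also speaks of observed responders, while the rule does not say whether observed or imputed responders trigger it. Two programmers could produce different tables for an endpoint in the testing hierarchy.

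**Working it through.** The plan prints no interval to reproduce, so the check applies its formulas to plausible counts.

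**Inputs**
- 95% two-sided, z = 1.96 (SAP 8.1.2).
- 50 subjects per CZP group and 25 on placebo (Protocol 14.8.1).
- PGA response at Week 12 in the Phase 2 study: placebo 1.7%, CZP 52.5% and 72.4% (Protocol Table 5-2). No Week 16 PGA planning rate is stated, so placebo 1.7% to 5% is an assumed range.
- PASI75 on placebo 15% (Protocol 14.8.1).
- No missing data. Between-imputation variance would slightly reduce the ratios below.

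**1. The two formulas differ.** Without a covariate the ordinary formula reduces to the unpooled one. At 15% and 70%:
- unpooled √(0.15×0.85/25 + 0.70×0.30/50) = 0.0964
- pooled, p = (3.75+35)/75 = 0.517: √(0.517×0.483×0.06) = 0.1224

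This pair matters too. If the other CZP group is the degenerate one, the trigger puts this comparison on the pooled formula as well, with a ratio of 1.27.

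**2. Intervals at 0/25 on placebo.** For 36/50, p = 36/75 = 0.48, SE = √(0.48×0.52×0.06) = 0.1224, and 0.72 ± 1.96×0.1224 gives 48% to 96%. For 26/50, p = 0.347, SE = 0.1166, and 0.52 ± 0.2285 gives 29% to 75%. Agresti-Caffo adds one responder and one non-responder to each group. For 36/50 this gives 37/52 − 1/27 = 0.675, SE 0.0726.

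| CZP | SAP pooled | Newcombe | Agresti-Caffo | SAP width ÷ Newcombe width |
|---|---|---|---|---|
| 26/50 | 29–75% | 33–65% | 33–64% | 1.42 |
| 36/50 | 48–96% | 53–83% | 53–82% | 1.62 |

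**3. Jump between routes.** Moving from 0/25 to 1/25 on placebo:
- 36/50: width falls from 0.48 to 0.29 unadjusted, or 0.29–0.32 with the prior-biologic term.
- 26/50: width falls from 0.46 to 0.32 unadjusted, or 0.32–0.36 with that term.

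The adjusted figures assume a balanced covariate with 20% to 40% exposed. The cut runs from 22% (0.457 to 0.356) to 39% (0.480 to 0.293).

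**4. Impossible limits.** At 38/50, 0.76 + 1.96×0.1225 is just above 1. At 40/50 the interval is 56% to 104%. The chance of 38 or more out of 50 at a true rate of 72.4% is 35%.

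**5. Coverage given 0/25**, summed over the binomial for CZP at 52.5% and 72.4%, with placebo at 1.7% to 5%:
- SAP: 99.6% or more
- Newcombe: about 97% to 99%
- Agresti-Caffo: about 96% to 97%
- Agresti-Caffo SE placed around the raw difference: 91.5% to 95.6%
- plain unpooled interval: about 85% to 95%, because it gives placebo zero variance

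**6. Chance of 0/25 on placebo.** PGA: 0.983²⁵ = 65% and 0.95²⁵ = 28%. PASI75: 0.85²⁵ = 1.7%.

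**7. Where the direction changes.** The excess width fades at low CZP rates: the SAP/Newcombe ratio is 1.13 at 10/50 and 0.93 at 5/50. At a true CZP rate of 5% and placebo at 0.5% to 3%, pooled coverage falls to about 92%. If a CZP group is 50/50, the pooled SE exceeds the unpooled one only below 10/25 placebo responders.

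**8. The bullet.** Presenting the rates as 0 or 1 makes sense only if every group is empty or full. The exact-regression rules and the two-group bullet all keep the calculations when fewer groups are degenerate. The *all groups* reading is therefore the coherent one, but the text does not say so.

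**The case against.** The interval is supplementary. Protocol 14.3.1 promises only the odds ratio and its interval, and hierarchy p-values come from the (exact) logistic regression. At plausible rates the error is conservative, and for PASI75 the chance of reaching the rule through an empty placebo group is only 1.7%. All of this stands, and it limits the importance of the point.

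The coverage in step 5 is conditional on 0/25. Averaged over both routes (no covariate or imputation, same rates), the SAP covers about 97% to 99%. With Agresti-Caffo in the fallback it covers about 96% to 97%, a change of 0.6 to 2.3 percentage points. That is a fair dilution, but the table that gets published is the conditional one, and there the interval is plainly too wide.

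Read literally, the first bullet would suppress the interval at 0/25. That is possible, but it contradicts the rest of the section and is itself a reason to edit it.

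The remedy does not make the methods identical. Agresti-Caffo is centred off the raw difference and can still exceed 100%, from 48/50 rather than 38/50. Narrowing a prespecified interval after an unblinded interim also has a credibility cost. These points stand as costs of the change; they do not justify an equal-rates variance in an interval for unequal rates.

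**Conclusion.** The point holds. The fallback interval uses the wrong variance for its purpose and is inconsistent with the ordinary route. With 0/25 on placebo and CZP near the Phase 2 PGA rates, it is 1.4 to 1.6 times as wide as Newcombe's interval and covers at least 99.6% instead of 95%. These figures assume the planned group sizes, complete data and Phase 2-like rates; the chance of reaching the rule for PGA depends on the assumed placebo rate. Type I error, gatekeeping and the odds-ratio p-values are untouched. What is at stake is the stated precision of an effect size for hierarchy endpoints, PGA in particular. It should be corrected, but it does not threaten the trial's conclusion.

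**What to change.** In the no/only-responder case:

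1. For each imputation, pass the Agresti-Caffo adjusted difference together with its unpooled standard error to PROC MIANALYZE. Passing the standard error alone, around the raw difference, can under-cover.
2. If all imputed data sets are identical, apply that interval, or Newcombe's, once to the observed data. The SAP names no risk-difference standard error for that case.
3. Keep raw responder proportions as point estimates and footnote that the interval is not centred on the raw difference (centre 0.48 against 0.52 at 26/50; 0.68 against 0.72 at 36/50).
4. In the first closing bullet, change *any* treatment group to *all* treatment groups, and state whether observed or imputed responders trigger the rule.

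The cost is SAP wording and a few lines of code; exact-regression p-values do not change. SAP 4.3 and Table 8-4 make the Week 16 analyses the same at interim and final, and SAP 9.3 already cites interim results. The change must therefore be labelled as post-interim, or the currently specified interval shown alongside. If the fallback was used at the interim, the two reports will show different intervals and should say why.
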